### **E. Complications**

1. As when caring for any woman in labor, the health care professional is responsible for using clinical judgment to respond appropriately when complications arise. If deviations from normal during immersion are observed, the woman should be asked to exit the tub and assisted out of the water for further assessment as necessary to perform standard care assessments and interventions.

A. *Tight nuchal cord:* If a tight nuchal cord cannot be reduced, and the somersault maneuver is ineffective, the woman should be assisted to stand above the water so

the cord can be clamped and cut to facilitate birth out of the water. **Under no circumstances should a nuchal cord be clamped and cut under water.** The woman should remain standing to give birth to the rest of the body and to avoid submersion of the neonate's head after birth. The tub will be drained.

B. *Shoulder dystocia*: If a shoulder dystocia occurs in the tub and cannot be resolved with position change, assist the woman out of the tub to complete the birth. Once the neonate's head is exposed to air, it should not be re-submerged.

C. *Excessive bleeding*: The presence of excessive bleeding into the water should prompt the immediate evaluation of the source. According to Waterbirth International, the water should never be dark enough that the woman is not visible through the water. In the case of excessive bleeding, assist the woman out of the tub for further evaluation. Initiate quantification of blood loss to more accurately assess blood loss volume. Excessive bleeding or blood loss will be determined based on the color of the water in the tub. Obstetricians, midwives, and nursing staff will be taught to evaluate the amount of bleeding prior to the start of the study. There should be minimal bleeding prior to the birth of the baby, and more than minimal bleeding in the first stage of labor should prompt the team to assist the woman out of the water.

D. *Umbilical cord avulsion*: If cord rupture is suspected, the cord should be immediately clamped at the umbilicus and cut. Cord clamps must be readily available. If cord rupture is confirmed, the newborn should be removed from the tub for assessment.

E. *Loss of consciousness*: Emergency procedures must be enacted immediately, and the woman should be removed from the tub quickly and safely. Assign one person to ensure the woman's head remains above the water surface at all times and activate the emergency response team to help lift the unconscious woman out of the tub and to initiate emergency evaluation and treatment.

## VI. STANDARD LAND BIRTH PROTOCOL

Women randomized to the land birth group will be admitted to L&D as inpatients and will be cared for using routine standards of care, consistent with practice guidelines from ACNM/ACOG/AWHONN. Standard labor options (pain control, positioning, monitoring) will be offered to women in accordance with their particular labors and needs.

## VII. STATISTICAL PLAN

The **primary outcome** we seek is a reduction of IV narcotic and epidural anesthesia use. We anticipate that this pilot project would be powered to detect a very clinically meaningful percentage point reduction in use of IV narcotic and epidural anesthesia. We carried out a power analysis using G\*Power 3.1.9.6. Using the Fleiss methodology to estimate power calculations with 80% power at the 0.05 level of significance, we estimate the following: to detect about 80% reduction in IV narcotic use from 24.5% down to 5.5%, estimated need would be 68 in the waterbirth group, 34 in the control group. To detect about 40% reduction in epidural use from 59% down to 34%, estimated need would be 74 in the waterbirth group, 37 in the control group. We have recalculated our sample sized based on the current enrollment attrition rate of 39.4%

(rate in which patients risk out of the study). With a 2:1 allocation ratio, approximately 120 subjects were initially earmarked to be recruited into the study given 74 would be needed in the waterbirth group and 37 would be needed in the land birth group to detect a 40% reduction in epidural use. Following the recommendations of Sakpal, we used the attrition rate (rate in which patients risk out of the study) to calculate adjusted sample sizes as 124 in the waterbirth group and 62 in the land birth group for a total of 186. We continue to approach most pregnant people eligible for waterbirth with the understanding that some will not want to participate in a research study. The results of this pilot should inform sample size required for a larger, definitive study that would be powered to detect smaller, still meaningful reductions in narcotic/epidural use.

We will compare baseline characteristics and pre-determined outcomes between patients who are randomized to either waterbirth or land birth. We will compute frequencies, means with 95% confidence intervals, and medians with interquartile ranges, as appropriate per variable type. Differences among the groups will be tested using the Pearson chi-squared test of independence (or Fisher's exact), Student's t-test, or Wilcoxon's rank sum test, respectively. Continuous variables will be assessed for normal distribution. Categorical variables will be assessed for collinearity. Potentially, we will use logistic regression for binary categorical outcomes (e.g., opioid use/anesthetist intervention, maternal tears, vaginal birth versus conversion to cesarean section, etc.) and linear regression for continuous outcomes (e.g., blood loss, time to skin-to-skin contact, etc.). Potentially, we will also perform ordered logistic regression on ordinal outcomes such as satisfaction level and APGAR. All underlying assumptions will be tested for each statistical method used. A one tailed p value lower than 0.05 will be considered statistically significant.

Please note, a data safety monitoring plan has been created for this study and is included in Appendix D. The first ten subjects that are enrolled for a waterbirth will be monitored and reviewed by the study PI, co-investigators, and Maternal Newborn Quality Committee for any rare adverse outcomes. For all subjects, the Principal Investigator and co-investigators will continue to review all adverse outcomes and will regularly monitor the data to identify trends throughout the study.

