We initially aimed to enroll 120 patients in the study, 80 enrolled within the waterbirth group and 40 in the land group. We recognize that some women will risk-out or opt-out because of the unpredictability of labor and birth. Additionally, we aim to approach most patients eligible for waterbirth with the understanding that some women will not want to participate in a research study. We have recalculated our sample sized based on the current enrollment attrition rate of 39.4% (rate in which patients risk out of the study). With a 2:1 allocation ratio, approximately 120 subjects were initially earmarked to be recruited into the study given 74 would be needed in the waterbirth and 37 would be needed in the land birth group to detect a 40% reduction in epidural use. Following the recommendations of Sakpal, we used the attrition rate (rate in which patients risk out of the study) to calculate adjusted sample sizes as 124 in the waterbirth group and 62 in the land birth group for a total of 186.

Participants who are ineligible for waterbirth will be excluded from both the land or water groups, and no further data will be collected. Please note that given the variable nature of birth, once a woman is randomized and enrolled to either group and meets ongoing eligibility criteria, an intention to treat model will be used for analysis following the birth.

Study participation will be offered to women seeking routine prenatal care in the Midwifery and Wellness Clinic, Exclusively for Women, and the Women's Health Clinic at Aurora Sinai Medical Center at the beginning of the third trimester (25 weeks 0 days to 34 weeks 0 days gestation). Eligible patients will be consented by a research study coordinator (risks and benefits will be done by an Aurora UW Medical Group midwifery or obstetric provider [CNM or physician] listed on this protocol) following the patient's prenatal visit. Note, in rare cases midwifery or obstetric providers listed on this protocol may conduct full consent. Following voluntary consent, all study participants will be randomized (see above for randomization).

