### **A. Management of labor in water**

1. Before immersion, ensure that the woman is a candidate for warm water immersion based on inclusion and exclusion criteria
  - a.) The tub should be filled using ordinary tap water without additives (e.g., salt, essential oils, sanitizers).
  - b.) The water temperature should be assessed and documented hourly by nursing.
  - c.) During the first stage of labor in water, the water temperature should never exceed 37.7°C (100°F) and may be adjusted to cooler temperatures per the woman's preference.
2. The woman in labor may enter or leave the water at any point with assistance.
  - a) The woman should be instructed to use proper body mechanics when entering and exiting the tub and do so only with staff or a support person in attendance.
  - b) If complications or changes occur in the maternal or fetal condition that require further assessment or treatment outside of the tub, share this information with the family and assist the woman out of the tub.
3. Positioning for comfort in the tub is dependent on the preferences of the woman and the judgment of the provider in consultation with the woman.
4. Provide hydration in the form of oral liquids or intravenous (IV) fluids as indicated. All IV or saline lock sites should be covered with an occlusive, water-resistant dressing while the woman is in the tub.
5. The well-being of the woman and fetus are assessed and managed in accordance with practice protocols for *any other woman* during labor, including monitoring maternal vital signs, assessing the fetal heart rate and initiating intrauterine resuscitation strategies when indicated (e.g., maternal position changes and IV fluid bolus for fetal heart rate changes or Category II fetal heart rate).

- a.) A waterproof Doppler or waterproof electronic fetal monitoring equipment should be used to assess the fetal heart rate.
- b.) Waterproof electronic fetal monitoring equipment may be used to verify or clarify if an indeterminate fetal heart rate pattern is present, and this can guide management.
- c.) Management of indeterminate fetal heart rate patterns depend on multiple factors. Intrapartum resuscitation techniques such as position change, hydration, and correction of hypotension or tachysystole are instituted as necessary.

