## **B. Management of the second stage of labor**

1. The woman may choose any position in the tub or pushing during the second stage of labor that feels comfortable and that is deemed safe by the attending provider or registered nurse. The health care professional may request adjustments to the position to facilitate observation of progress and/or to maintain assessment of maternal and fetal wellbeing. Additionally, the health care professional will document that they are comfortable proceeding with the subject in the study once in the second stage of labor through a dot phrase (waterbirthsecondstage Appendix A).
2. Water temperature
  - a.) During the second stage of labor, the water temperature should never exceed 37.7°C (100°F) and may be adjusted based on the woman's preference within a narrow range of 36.1°C to 37.7°C (97.0°F to 100°F).
3. Maternal and fetal well-being should be assessed and documented as they would be for a conventional (land) birth
4. Fetal heart rate and contraction pattern are assessed in accordance with standard of care recommendations, generally every 5 to 15 minutes (in accordance with AWHONN/ACOG guidelines).
5. Supporting birth of the neonate
  - a.) The woman should be supported in the use of spontaneous, physiologic pushing.
  - b.) The health care provider may use a hands-off or hands-poised position to facilitate birth by controlled, spontaneous, pushing efforts; a hands-on method of birth management may be employed when indicated.
  - c.) It may not be necessary to feel for the presence of a nuchal cord if the birth of the body quickly follows the head. Loose nuchal cords and other entanglements can be resolved as the neonate is born underwater before the first breath
  - d.) The time of birth will be noted when the neonate's entire body is outside of the woman.
  - e.) The neonate must be born completely underwater without exposure to air until the face is brought gently and directly to the surface. The neonate's head **must not** be re-submerged under water after it has been brought to the surface.
  - f.) If a woman raises herself out of the water and exposes the head of the fetus to air, she should be assisted/supported to remain out of the water to avoid the potential risk of the neonate gasping underwater with re-submersion.

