  - g.) After birth, assist in bringing the neonate directly and gently to the surface (within 5–10 seconds) to minimize tension on the umbilical cord and to reduce the possibility of avulsion. Cord clamps should be readily available.
  - h.) Maintain warmth of the neonate through skin-to-skin contact with the woman

and submersion of the neonate's lower extremities, abdomen, and chest. Dry the neonate's exposed head to reduce heat loss.

i.) Apgar scores should be obtained at one and 5 minutes after birth per routine standards.

j.) In the presence of stable newborn status and transition to extrauterine life, care of the cord can follow best practices to support delayed cord clamping.

k.) If neonatal resuscitation measures are indicated and this is not possible without cutting the cord the cord should be clamped and cut, and the neonate removed from the water immediately and brought to the infant warmer.

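### The final safety comparison is by randomized arm only, so any added cord-injury risk from birth in water is diluted, and outcomes of women who become ineligible in the tub can be lost

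*Combined protocol and SAP*

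**What the plan says.** **Comparison.** Section VII (Statistical Plan): "We will compare baseline characteristics and pre-determined outcomes between patients who are randomized to either waterbirth or land birth". Section IV defines who is analysed: "once a woman is randomized and enrolled to either group and meets ongoing eligibility criteria, an intention to treat model will be used". Women who risk out are handled differently: "Participants who are ineligible for waterbirth will be excluded from both the land or water groups, and no further data will be collected". Section III, however, keeps a woman excluded by the birth attendant in her allocated group.

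**Leaving the water.** Section V.A: "The woman in labor may enter or leave the water at any point with assistance". Section V.E also moves women out for some complications; for example, if shoulder dystocia "cannot be resolved with position change, assist the woman out of the tub to complete the birth". In Section VII (Data Collection), maternal item p records a switch from water to land and the reason, with no analysis attached. Study item 1b gives wanting to leave the water as an example of withdrawing from participation.

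**The harm.** Section V.B has the neonate brought straight to the surface "to minimize tension on the umbilical cord and to reduce the possibility of avulsion". Section V.E lists cord avulsion among the complications: "If cord rupture is confirmed, the newborn should be removed from the tub for assessment". Hypothesis 4a names umbilical cord injury, and there is a yes/no field for it. Section VIII also lists cord avulsion among the risks of any vaginal delivery.

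**Monitoring.** The data safety monitoring plan reviews the first ten completed waterbirths, then adverse outcomes in all subjects. Only the first-ten review is defined by actual birth in water, and it has no land comparator.

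**The concern.** Hypothesis 4a expects infants in the waterbirth group to fare no worse than those in the land group. For a risk that birth in water adds, counting land births in the water arm shrinks the observed difference in the direction of that hypothesis. The result then depends partly on how many women switched.

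Section VIII foresees a multi-center trial and adoption by other hospitals. Those readers need the number of cord injuries among infants actually born in water, and how large a risk that number leaves possible. A limit calculated on the whole arm looks tighter than the in-water data support.

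The rule that ends data collection is a second route to the same gap. A woman who becomes febrile or hypertensive, or passes fluid that is not clear, after entering the tub meets a listed reason for ineligibility. On the words of Section IV, her outcomes and her infant's need not be collected, although both were exposed.

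**Working it through.** **1. The plan's own figures.** A one-sided Fleiss calculation for 59% against 34%, 2:1, without continuity correction, gives 72 water and 36 land; the plan states 74 and 37. Dividing by 1 − 0.394 gives 74/0.606 = 122.1 and 37/0.606 = 61.1, so 123 and 62; the plan states 124 and 62. Going back, 124 × 0.606 = 75.1, so about 74 analysed water-arm women is the right planning figure.

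**2. Dilution.** Let f be the share of analysed water-arm women who give birth in water, r_w the risk in water and r_l the risk on land. Assume water-arm births out of the water carry r_l.

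Arm risk = f·r_w + (1 − f)·r_l

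By-arm excess = f·(r_w − r_l)

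The factor is f whether or not r_l is zero, so a background risk of avulsion on land does not remove the dilution.

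**3. Illustration.** The documents give neither f nor a cord-injury rate. Assume 74, 59, 44 or 37 births in water and a true excess of 5 points. With zero events in n births, the exact two-sided 95% upper limit is 1 − 0.025^(1/n).

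| Births in water | f | By-arm excess (true 5 points) | Upper limit, births in water | Ratio to limit on 74 |
|---|---|---|---|---|
| 74 | 1.00 | 5.0 | 4.9% | 1.0 |
| 59 | 0.80 | 4.0 | 6.1% | 1.2 |
| 44 | 0.59 | 3.0 | 8.0% | 1.7 |
| 37 | 0.50 | 2.5 | 9.5% | 2.0 |

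The first-ten review, with zero events, has an upper limit of 1 − 0.025^(1/10) = 30.8%.

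**4. Would the test change?** Take a 5% in-water risk, no land events, 37 land women and a one-sided Fisher exact test at 0.05. By arm (74 v 37), 8 events to 0 are needed.

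| Births in water | Power by arm | Power on births in water |
|---|---|---|
| 74 | 3.1% | 3.1% |
| 59 | 0.9% | 7.4% |
| 44 | 0.2% | 6.7% |
| 37 | 0.05% | 3.6% |

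Neither analysis could detect the harm.

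**5. Women whose data collection ends.** Planned water-arm risk-outs: 0.394 × 124 = 48.9, about 49. How many occur after tub entry is not given. At an assumed 5%, 10% or 20%, it is 2.4, 4.9 or 9.8, so about 2, 5 or 10 women.

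**The case against.** Intention to treat is the right main comparison for a randomized trial, and planning it is not an error. The trial is a feasibility pilot that tests hypotheses only if numbers allow, and step 4 shows that dilution is not what limits it. Continued review covers all entered data and logs every adverse outcome, so an avulsion would be noticed individually and could be tied to place of birth through item p. Births completed in water are also a selected group, because women with complications are taken out, so a table of them may look too reassuring. All of this stands. It limits the point to a missing descriptive denominator and interval.

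The dilution itself is uncertain. If item 1b means that women who choose to leave the water are treated as withdrawn, fewer land births remain in the water arm. That also stands, but those women were exposed in the tub, and their outcomes might then be missing from the comparison.

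On data collection, Sections V.A and V.E speak of leaving the tub, not the study, and Section V.A manages Category II tracings with resuscitation measures. Problems in the tub therefore need not trigger exclusion. But nothing limits the Section IV rule to the period before tub entry, and Section III says something different for attendant exclusions.

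**Conclusion.** The point holds as a minor one. The plan has no count or interval by actual place of birth, and any excess of cord injury from birth in water is multiplied by an unstated share f. Over the assumed range, the zero-event upper limit for births in water is 1.0 to 2.0 times the 4.9% that the whole arm gives. The dilution formula assumes that water-arm births on land carry the land risk. The loss of exposed women's outcomes is possible on the wording; its size is unknown.

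A reader might infer more than the documents support:

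- *Cord avulsion happens only in water.* Section VIII lists it for any vaginal delivery. Sections V.B and V.E support an added in-water route, and only that added risk is diluted.
- *The Hypothesis 4a test would come out differently.* Power is about 7% or less either way in the 5% scenario.
- *The 39.4% risk-out rate is the dilution.* Under Section IV those women leave the analysis; the dilution comes from eligible women who switch.
- *All safety outcomes are affected.* NICU admission, low Apgar scores and infection do not need birth under water, and the documents name no such maternal harm for Hypothesis 2a. Section V.B does name another in-water risk, advising that a woman stay out of the water "to avoid the potential risk of the neonate gasping underwater with re-submersion", but that event has no field of its own.

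**What to change.** 1. Change Section IV to: *For any woman who becomes ineligible or leaves the water after entering the tub, delivery and newborn safety outcomes will still be collected and reported.* Align Section III and item 1b with this, so that leaving the water is not by itself a withdrawal from data collection.

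2. Keep the intention-to-treat comparison and add to Section VII (Statistical Plan): *For the Hypothesis 4a neonatal events, chiefly cord injury, one descriptive, non-randomized table will give counts and exact 95% confidence intervals for births completed in water and for water-arm women who entered the tub but gave birth out of it, beside the land arm, with switch reasons from item p. Births completed in water are selected toward uncomplicated births.*

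The cost is a sentence, a short paragraph and one table, with IRB approval for the protocol change. Item p, the hourly tub-temperature sheets and the labor progress notes supply most of the inputs. The downsides are that the groups are not randomized, that tub entry may be incompletely recorded because no entry or exit time is among the listed variables, and that outcomes of women already removed may be missing. The number missing should be reported.

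### For low-rate binary outcomes such as IV narcotic use, the unspecified choice between Pearson and Fisher should be replaced by one pre-stated test per outcome; Boschloo's exact test would gain about 5 points of power over Fisher at 74/37

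*Combined protocol and SAP*

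**What the plan says.** All of this is in section VII (Statistical Plan) unless noted.

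- **Test.** Categorical outcomes are compared with the "Pearson chi-squared test of independence (or Fisher's exact" test. No rule says which applies when. Logistic regression is mentioned only as a possibility.
- **Level.** "A one tailed p value lower than 0.05 will be considered statistically significant".
- **Sizing.** "Using the Fleiss methodology to estimate power calculations", "with 80% power at the 0.05 level of significance". For IV narcotic use, 24.5% on land against 5.5% in water, "estimated need would be 68 in the waterbirth group, 34 in the control group". For epidural use, 59% against 34%, "estimated need would be 74 in the waterbirth group, 37 in the control group". The epidural figure governs. It is inflated for 39.4% attrition to 124 and 62.
- **Outcomes.** Section II (Specific Aims) makes lower use of IV narcotics and epidural anesthesia the primary outcome. Hypotheses 2a and 4a state that waterbirth will bring no excess of maternal or neonatal adverse outcomes. No expected harm rates are given.
- **Who is analysed.** Section IV (Study Design) says that women who become ineligible for waterbirth leave both groups, with no further data collected. The planned analysed sample is therefore about 74 and 37.

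**The concern.** With 2:1 allocation and a low event rate, the land-arm count is small. In that range Pearson's large-sample approximation and Fisher's conditional test can give different answers on the same table. The plan leaves the choice open there, for one of its two named primary measures. If the choice follows the observed counts, as is customary, the data decide which test is used, and the procedure has neither test's known properties.

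The choice affects both error and power. Fisher spends well under the allowed 5%, so power is lost. One-sided Pearson can spend slightly more than 5% in the direction that favours waterbirth. For adverse outcomes, an over-conservative test makes a true excess harder to see, in a trial that hopes to find none.

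**Working it through.** **1. Reproducing the plan's sample sizes.** Inputs are the rates, 80% power, 0.05 and the 2:1 ratio, all from section VII. The formula is the Fleiss pooled-variance one without continuity correction, one-sided, with the pooled rate p̄ taken as the simple average of the two rates:

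n(land) = [1.645·√(1.5·p̄(1−p̄)) + 0.8416·√(p₁(1−p₁) + p₂(1−p₂)/2)]² / (p₁−p₂)²

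- IV narcotic: p̄ = 0.15. (1.645·√0.19125 + 0.8416·√0.21096)² / 0.19² = 1.223/0.0361 = 33.9, so 34 land and 68 water.
- Epidural: p̄ = 0.465. (1.645·√0.37316 + 0.8416·√0.3541)² / 0.25² = 2.267/0.0625 = 36.3, so 37 land and 74 water.
- Inflation: 37/(1−0.394) = 61.1, so 62 land and 124 water.

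All three match the plan. The sizing therefore corresponds to an uncorrected, one-sided Pearson-type test, not to Fisher's.

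**2. Expected counts at 74/37.** The pooled IV narcotic rate is (74×0.055 + 37×0.245)/111 = 13.135/111 = 11.8%. The expected land-arm count is 37×0.1183 = 4.4 (4.0 at 68/34, 7.3 at 124/62). For epidural use the pooled rate is (74×0.34 + 37×0.59)/111 = 42.3%, and the expected land-arm count is 15.7.

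**3. Exact error and power.** Each rule is evaluated by summing the product of the two binomial probabilities over every possible table that the rule rejects. Size is maximised over a grid of 2,000 common event rates. The switching rule (Fisher if the smallest expected count is below 5, otherwise Pearson) is an assumption, because the plan states none. Under the planning rates at 74/37 it selects Fisher with probability 0.67.

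IV narcotic use at 74/37, one-tailed 0.05, waterbirth lower:

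| Test | Error at 11.8% | Maximum error | Power, 5.5% vs 24.5% |
|---|---|---|---|
| Fisher | 2.8% | 3.5% | 81.2% |
| Pearson, uncorrected | 5.6% | 6.7% | 88.9% |
| Switching rule | 3.6% | 5.5% | 82.7% |
| Boschloo | at most 5% | 4.99% | 86.3% |

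Boschloo's gain over Fisher is 86.3 − 81.2 = 5.1 points. Over the switching rule it is 86.3 − 82.7 = 3.6 points.

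**4. Other sample sizes, same rates.**

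| Water/land | Fisher | Boschloo | Gain |
|---|---|---|---|
| 68/34 | 77.5% | 82.2% | 4.7 |
| 80/40 | 84.5% | 87.9% | 3.4 |
| 124/62 | 95.9% | 96.8% | 0.9 |

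At 124/62 the switching rule gives 97.5%, slightly more than Boschloo. If the tests were two-sided, the gain over Fisher would be 2.6 points at 68/34 and 2.0 at 74/37.

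**5. Harms.** The rates below are assumptions, and the tail is taken as waterbirth higher. Power at 74/37:

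| Land vs water | Fisher used | Fisher | Switching rule | Boschloo |
|---|---|---|---|---|
| 3% vs 12% | 93% | 33% | 34% | 43% |
| 5% vs 20% | 29% | 64.6% | 70.3% | 71.7% |
| 10% vs 25% | 3% | 52% | 61.1% | 61.2% |

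At 2% vs 4%, Fisher gives 0.5% and Boschloo 1.4%. In this direction no test is inflated: at a common rate of 5%, the real error is 0.5% for Fisher, 2.6% for Pearson and 1.3% for Boschloo.

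**6. Epidural use.** At 74/37 Pearson gives 80.6% and Boschloo 80.1%. At 124/62 they give 95.0% and 94.6%. Boschloo brings no gain here.

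**The case against.** Pearson with Fisher for small counts is conventional. The plan also says it will check the assumptions of each method, which points to a choice based on expected counts. This is a feasibility pilot that will test hypotheses only if numbers allow, so a few points of power do not change its purpose. These points lower the weight of the concern. They do not supply a rule, and a choice made on expected counts is still made on the data.

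Four stronger readings are tempting, and none is supported.

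- **That neither test holds 5%.** Fisher does: its maximum is 3.3% to 3.6% at 68/34, 74/37 and 124/62. Only one-sided Pearson exceeds 5% appreciably at low rates, and only in the benefit direction. Its highest values occur at event rates of about 3 to 5%, where the customary trigger would usually select Fisher.
- **That IV narcotic use is underpowered.** Fisher gives 77.5% at 68/34, but the governing evaluable sample is 74/37, where it gives 81.2%. The Fleiss method does not presuppose Fisher.
- **That Boschloo gains a large amount for every harm at no cost.** Against the switching rule the gain is about 9 points at 3% vs 12%, 1.4 at 5% vs 20% and 0.1 at 10% vs 25%. For very rare events the limit is sample size. Boschloo also has less power than uncorrected Pearson for IV narcotic use (86.3% vs 88.9% at 74/37), because Pearson overspends its error allowance.
- **That a better test would establish safety.** No test of difference shows the absence of excess harm. Hypotheses 2a and 4a are not answered by a non-significant result from any of these tests.

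**Conclusion.** The point holds in a limited form. For IV narcotic use, a named primary measure, the plan leaves open a choice between a conservative test and a slightly liberal one, and the observed counts may settle it. At 74/37 Boschloo's exact test keeps error at or below 5%. It adds 5.1 points of power over Fisher and 3.6 over the switching rule. It is never less powerful than Fisher.

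The size rests on three assumptions: an analysed sample near 74/37 (at 124/62 the gain over Fisher is 0.9 points and the switching rule is marginally ahead), one-tailed testing as the plan states, and the expected-count-below-5 trigger. For harms, the benefit depends on rates that the documents do not give, and ranges from negligible to about 9 points over the switching rule in the scenarios shown. The change is worth making because it is cheap and removes a data-dependent choice. The existing plan is not invalid without it.

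**What to change.** In section VII (Statistical Plan), replace the open choice with a test fixed by outcome before the data are seen:

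- IV narcotic use, and a listed set of adverse outcomes expected to be uncommon: Boschloo's unconditional exact test, with the tail stated for each.
- Epidural use: Pearson's chi-squared test, since the expected land-arm count is about 15.7 and Boschloo offers no gain.
- The choice does not depend on observed counts.

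In the sample-size paragraph of the same section, state the IV narcotic power for the chosen test: 82.2% at 68/34 and 86.3% at 74/37, one-tailed 0.05. Add that a non-significant difference in adverse outcomes will not be read as support for Hypotheses 2a or 4a.

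The cost is a few sentences, using a test available in standard software. No more women or data are needed. The one statistical cost is a little power relative to uncorrected Pearson for IV narcotic use: 88.9 − 86.3 = 2.6 points at 74/37.
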